## Outcome Measures

Study outcomes and mediating factors are detailed in Table 1. Primary outcomes across all patients will include patient reported outcomes (PROs) of stool frequency, stool consistency, pain interference and GI symptom severity (see Appendix D), and fecal calprotectin. Secondary outcomes will include patient-reported disease activity scores as measured by the Pediatric Ulcerative Colitis Activity Index (PUCAI) and Short Crohn's Disease Activity Index (SCDAI), clinically-evaluated disease activity scores contained in ICN registry (PUCAI and sPCDAI), growth, laboratory markers of inflammation and disease status [C Reactive Protein (CRP), Hematocrit, Erythrocyte Sedimentation Rate (ESR), Albumin]. Fecal calprotectin was selected as the central marker of intestinal inflammation because it correlates well with both clinical and histologic remission, is noninvasive and objective, and has been shown to be a useful tool to monitor response to therapy. Safety Outcomes: The major safety concerns for patients with IBD participating in a diet intervention include weight loss and inadequate nutrition. Weight loss typically occurs within the first few weeks of starting the diet. Weight will be assessed at all clinic visits and at the dietitian follow up visits (weeks 4 and 12) and by weekly weights entered in the Eureka app if there is a home scale available. If a home scale is available, patients will be instructed to obtain an initial weight on their home scale at the beginning of the baseline period and use the same home weighing scale throughout the study period. Nutrition intake will be monitored by the dietitian regularly for all enrolled patients and will be assessed via 3-day diet diaries conducted at specified intervals (baseline and in weeks 3-5 of each treatment period) and weekly weight tracking (if available). In addition, we will collect results of any serum Vitamin D level monitoring conducted as part of routine care and will report these results to the DSMB. Mediating factors: We will collect demographic data from the ICN registry including age, gender,

## USING SINGLE SUBJECT (N-OF-1) DESIGNS TO ANSWER PATIENT-IDENTIFIED RESEARCH QUESTIONS – AIM 1

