### **3.5.4 Early Withdrawal of Participants**

If a patient experiences symptom flare, leading to either the diet intervention being stopped, medication being changed, or the need for surgical intervention, their participation in the N-of-1 protocol will be discontinued. In addition, patients who become pregnant during the study will be automatically withdrawn, as will patients that have  $\geq 7.5\%$  nonintentional weight loss. Patients may also withdraw if they feel that they are unable or unwilling to continue the assigned diet or data collection. Participants will be dropped from the study if they have a symptom tracking response rate of  $<50\%$  in the baseline period that does not improve after reasonable attempts by research coordinators (as outlined in the study SOPs) to assist participants in improving data collection. Because completion of stool fecal calprotectin is required to advance from one treatment period to another, a participant who never collects and sends in a stool specimen will be dropped at that point in the study. All data from such participants will be retained and analyzed. Patients who wish to terminate a treatment period early (and switch to the next assigned treatment) will not be considered withdrawals. Participants who wish to end their study participation early, but have completed at least two full diet treatment periods (i.e., A1 and B1), will have the option to discontinue participation and terminate the protocol early. Participants who choose to discontinue from the study in these instances will schedule a time to come into clinic to

receive their final study results and complete the end of survey questionnaire regarding their N-of-1 experience. These participants will not be considered withdrawals.

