**Missing data:** Based on our experience, the overall completion rates of daily symptom trackers and weekly surveys by ICN patients and parents is >80%, we have found that when participants are working on a specific test or personal experiment with their physician, adherence increases to >90%. In cases of missing outcome data, we will ignore the missing values in the analysis of individual N-of-1 trials which is equivalent to treating them as being missed at random since the analysis is not adjusted for covariates. In the meta-analysis, we will explore the association of missingness with observed variables and condition analyses on these variables as appropriate. We will also explore treating the missing observations as latent parameters and estimate them as part of the Bayesian model assuming them to be missing at random. If patients decide to stop a treatment before 8 weeks, we will analyze the data available. Since effect modifiers in the meta-analysis are collected at the patient level, we expect them to be completely collected (e.g., there will not be a need for a statistical approach to address missing data for these variables). In the meta-analysis, we will perform the following sensitivity analyses for different types of missing data:

(1) analysis of all available data; (2) analysis excluding patients who withdrew early from the trial; (3) analysis of patients who completed the entire protocol, i.e. excluding those who withdrew early and those who terminated any treatment periods early.

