### **3.8.5 Patient Surveys and Questionnaires**

Surveys and questionnaires to collect patient reported outcomes data (as described in Table 1) will be administered through the Eureka N-of-1 app, weblink, or paper/pencil as previously described. Symptom tracker and PRO questions that will be administered through the Eureka app are documented in Appendix D. The surveys to assess experience with the N-of-1 app are provided in Appendix H. The questions to assess baseline expectations are provided in Appendix C.

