## Appendix D: Symptom Trackers

### Daily Symptom Trackers – Patient Version

Stool Consistency	What have most of your stools looked like today?  Bristol Stool Chart  
  
 Type 1		Separate hard lumps, like nuts (hard to pass)	
 
 Type 2		Sausage-shaped but lumpy	
 
 Type 3		Like a sausage but with cracks on the surface	
 
 Type 4		Like a sausage or snake, smooth and soft	
 
 Type 5		Soft blobs with clear-cut edges	
 
 Type 6		Fluffy pieces with ragged edges, a mushy stool	
 
 Type 7		Watery, no solid pieces. Entirely Liquid	
  
	Type 1		Separate hard lumps, like nuts (hard to pass)	Type 2		Sausage-shaped but lumpy	Type 3		Like a sausage but with cracks on the surface	Type 4		Like a sausage or snake, smooth and soft	Type 5		Soft blobs with clear-cut edges	Type 6		Fluffy pieces with ragged edges, a mushy stool	Type 7		Watery, no solid pieces. Entirely Liquid
Type 1		Separate hard lumps, like nuts (hard to pass)																				
Type 2		Sausage-shaped but lumpy																				
Type 3		Like a sausage but with cracks on the surface																				
Type 4		Like a sausage or snake, smooth and soft																				
Type 5		Soft blobs with clear-cut edges																				
Type 6		Fluffy pieces with ragged edges, a mushy stool																				
Type 7		Watery, no solid pieces. Entirely Liquid																				
Stool Frequency	How many stools did you have today? [Enter Integer]																					

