### Daily Symptom Trackers - Parent Version

Stool Consistency	What have most of your child's stools looked like today?  Bristol Stool Chart  
  
 Type 1		Separate hard lumps, like nuts (hard to pass)	
 
 Type 2		Sausage-shaped but lumpy	
 
 Type 3		Like a sausage but with cracks on the surface	
 
 Type 4		Like a sausage or snake, smooth and soft	
 
 Type 5		Soft blobs with clear-cut edges	
 
 Type 6		Fluffy pieces with ragged edges, a mushy stool	
 
 Type 7		Watery, no solid pieces. Entirely Liquid	
  
	Type 1		Separate hard lumps, like nuts (hard to pass)	Type 2		Sausage-shaped but lumpy	Type 3		Like a sausage but with cracks on the surface	Type 4		Like a sausage or snake, smooth and soft	Type 5		Soft blobs with clear-cut edges	Type 6		Fluffy pieces with ragged edges, a mushy stool	Type 7		Watery, no solid pieces. Entirely Liquid
Type 1		Separate hard lumps, like nuts (hard to pass)																				
Type 2		Sausage-shaped but lumpy																				
Type 3		Like a sausage but with cracks on the surface																				
Type 4		Like a sausage or snake, smooth and soft																				
Type 5		Soft blobs with clear-cut edges																				
Type 6		Fluffy pieces with ragged edges, a mushy stool																				
Type 7		Watery, no solid pieces. Entirely Liquid																				

Stool Frequency - Parent Version	How many stools did your child have today? [Enter Integer]
----------------------------------	---

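### The daily Bristol item has no valid answer on a day without a stool, and the plan does not use the same-day stool count to set such days aside

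*Combined protocol and SAP*

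**What the plan says.** The Outcome Measures text in section 3.4 reads: "Primary outcomes across all patients will include patient reported outcomes (PROs) of stool frequency, stool consistency, pain interference and GI symptom severity", with fecal calprotectin as a further primary outcome. Table 1 gives both stool items as daily measures from the app.

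Section 3.8.5 makes Appendix D the record of what is asked: "Symptom tracker and PRO questions that will be administered through the Eureka app are documented in Appendix D". There, the daily tracker lists the consistency item first. It asks "What have most of your stools looked like today" and its options run from Type 1 (hard lumps) to Type 7 ("Watery, no solid pieces. Entirely Liquid"). The parent version has the same seven options. Neither version shows a no-stool answer or a skip rule. The stool count is listed next as an integer entry, so 0 can be recorded.

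Section 3.6.2 models ordinal outcomes with a cumulative logit link and says that the individual analyses run automatically once a trial ends. Its missing-data paragraph has one rule for all outcomes. Individual trials ignore missing values. In the meta-analysis the team will look at how missingness relates to observed variables, condition on them where appropriate, and explore "treating the missing observations as latent parameters and estimate them as part of the Bayesian model assuming them to be missing at random". It does not distinguish a day on which no stool existed from a day on which nobody answered.

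**The concern.** A family that has no stool to describe must either leave the item blank or pick a type. If it picks one, that answer enters the model as an observation of stool form, although there was none to observe.

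This ties two primary outcomes together. A diet that lowers stool frequency produces more zero-stool days. If those days tend to be given a particular type, consistency changes although the stools have not. The randomised comparison is exposed if the two diets differ in frequency, and so is each diet's comparison with baseline.

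Section 3.6.1 makes the individual patient's decision the primary goal, and each family receives an estimate and a probability of benefit for consistency. One family's habit of answering is not averaged out in its own trial. Patients with few stools can enter: sections 3.5.1 and 3.5.2 require evidence of inflammation and exclude severe activity, but set no minimum for symptoms.

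**Working it through.** The plan gives no figure on this point to reproduce. Its power statement concerns weekly PROMIS pain interference. The calculations below are illustrations, and each assumption is labelled.

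**1. Days at issue.** Section 3.3.1 gives four 8-week periods, and 3.6.2 discards the first 7 days of each. Analysed daily answers per full participant: 4 × (56 − 7) = 196. If zero-stool days make up 5%, 10%, 20% or 30% of days (assumed), then about 10, 20, 39 or 59 of the 196 have no true Bristol value.

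**2. Zero-stool days by mean frequency.** Assume Poisson counts, so P(0) = exp(−mean).

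| Mean stools a day | P(0) |
|---|---|
| 1 | 37% |
| 1.5 | 22% |
| 2 | 14% |
| 3 | 5% |

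**3. False shift in mean type.** Assume that frequency falls from 3 to 1.5 a day, that true form stays at type 5, and that Type 1 is entered on a fraction f of zero-stool days, with the usual type on the rest.

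Shift = f × [exp(−1.5) − exp(−3)] × (5 − 1) = f × (0.2231 − 0.0498) × 4 = f × 0.693.

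- f = 25%: 0.17
- f = 50%: 0.35
- f = 100%: 0.69

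All are towards harder stools. If the remaining zero-stool days are blank instead, the share of recorded answers that are false is f·p/(1 − p + f·p), where p = P(0). At f = 25% this is 0.067 against 0.013, a shift of 4 × 0.054 = 0.22. At f = 50% it is 0.126 against 0.026, a shift of 0.40. If every such day is blank or carries the usual type, the shift is about 0.

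**4. A second set of assumptions.** Take zero-stool days on 20% of days on one diet and 5% on the other, with identical form. The false difference is (0.20 − 0.05) × (entered type − true mean).

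- Type 1 entered: 0.15 × (1 − 4) = −0.45 at a true mean of 4; 0.15 × (1 − 5) = −0.60 at a true mean of 5.
- Type 4 entered: 0 and −0.15 respectively.

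**5. On the model's own scale.** A cumulative-logit fit to simulated data (20,000 days per diet, assumed cut-points) gave these log odds ratios:

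| Zero-stool shares | Handling | True | Estimated |
|---|---|---|---|
| 20% vs 5% | filled as Type 1 | 0 | −0.45 |
| 20% vs 5% | filled as Type 4 | 0 | −0.10 |
| 20% vs 5% | zero-stool days left out | 0 | 0.01 |
| 20% vs 20% | filled as Type 1 | −0.70 | −0.46 |

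The last row shows that equal shares do not make filling harmless: a true effect is diluted. Leaving the days out removes the false effect.

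**The case against.** Several points on the other side stand.

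- **Blanks do little harm.** Ignoring them compares stool form on days with a stool, which is what the remedy also does. A blank explained by a recorded count of 0 depends on observed data, and 3.6.2 lets the meta-analysis condition on observed variables. A reader might infer that blanks bias the diet effect, or that the plan will routinely estimate stools that never occurred. The documents support neither: individual trials ignore missing values, latent estimation is only to be explored in the meta-analysis, and the calculated shift from blanks is about 0.
- **Removal from the study does not follow.** Section 3.5.4 says: "Participants will be dropped from the study if they have a symptom tracking response rate of" less than 50% in the baseline period, and only after coordinators have tried to help. A reader might infer that a diligent family with few stools would be dropped. At a mean of 1 stool a day with every other day answered, Bristol completion is 100% − 37% = 63%, already above 50%. Pooled with a complete daily count it is (100% + 63%)/2, about 82%.
- **The harmful route stacks assumptions.** It needs families to enter a type, an atypical one, and (for a false effect rather than dilution) diets that differ in zero-stool days. The modified SCD adds a limited set of foods to the SCD, so a halving of frequency between the two is a strong premise. Real counts may also vary less than Poisson.
- **The app or the separate plan may already deal with it.** Section 3.6.2 calls itself an overview and defers to a separate statistical analysis plan. The app screenshots are not in the text reviewed, and row order in Appendix D does not prove screen order.

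What does not fall is the core. The item as documented has no valid answer on a zero-stool day, and the text reviewed gives no rule for an answer entered anyway.

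**Conclusion.** The point holds as a low-priority gap with a cheap and clearly better rule available. A type entered on a zero-stool day would be analysed as a real observation of a primary outcome, and could make consistency move with frequency.

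The size is unknown. The 0.17 to 0.69 range depends on the Poisson assumption, the fall from 3 to 1.5 stools a day, true form at type 5, and Type 1 being entered on 25% to 100% of zero-stool days. Under blank or typical answers it is about 0. The documents do not say how often zero-stool days occur or how families answer on them. If the app or the separate analysis plan already has such a rule, citing it closes the point.

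**What to change.** Add one sentence to section 3.6.2: when the same-day stool count is 0, stool consistency is not applicable, whatever was entered, and the day is excluded from the consistency model and from any estimation of missing values as latent parameters. The rule uses data already collected, can be applied to records already entered, and should be coded into the automated individual analysis.

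The cost is fewer analysable consistency days in patients with few stools, although none of the days lost had a stool to describe. The result then describes stool form on days with a stool, and reports should say so.

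A no-stool answer, or asking the count first and showing the Bristol item only when it is at least 1, would prevent the problem at source. It suits only cases where it can be introduced without changing the item partway through a participant's own trial, since measurement could then differ between that person's periods. The current protocol version is dated January 2020, after the 31 October 2019 end of enrolment given in the document history, so the analysis rule is the safer remedy.

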### Daily Symptom Trackers - Parent Version

Stool Consistency	What have most of your child's stools looked like today?  Bristol Stool Chart  
  
 Type 1		Separate hard lumps, like nuts (hard to pass)	
 
 Type 2		Sausage-shaped but lumpy	
 
 Type 3		Like a sausage but with cracks on the surface	
 
 Type 4		Like a sausage or snake, smooth and soft	
 
 Type 5		Soft blobs with clear-cut edges	
 
 Type 6		Fluffy pieces with ragged edges, a mushy stool	
 
 Type 7		Watery, no solid pieces. Entirely Liquid	
  
	Type 1		Separate hard lumps, like nuts (hard to pass)	Type 2		Sausage-shaped but lumpy	Type 3		Like a sausage but with cracks on the surface	Type 4		Like a sausage or snake, smooth and soft	Type 5		Soft blobs with clear-cut edges	Type 6		Fluffy pieces with ragged edges, a mushy stool	Type 7		Watery, no solid pieces. Entirely Liquid
Type 1		Separate hard lumps, like nuts (hard to pass)																				
Type 2		Sausage-shaped but lumpy																				
Type 3		Like a sausage but with cracks on the surface																				
Type 4		Like a sausage or snake, smooth and soft																				
Type 5		Soft blobs with clear-cut edges																				
Type 6		Fluffy pieces with ragged edges, a mushy stool																				
Type 7		Watery, no solid pieces. Entirely Liquid																				

Stool Frequency - Parent Version	How many stools did your child have today? [Enter Integer]
----------------------------------	---

**Weekly Symptom Trackers - Patient Version**

Weight (optional)	What is your current weight taken on your home scale in pounds? [Number]																																																																																														
PROMIS Pain Interference (patient $\geq$ 14 years)	
In the past 7 days...
 
  
 	Never	Almost Never	Sometimes	Often	Almost Always	
   
 I felt angry when I had pain.						
 
 0	1	2	3	4	
 
 I had trouble doing schoolwork when I had pain.						
 
 0	1	2	3	4	
 
 I had trouble sleeping when I had pain.						
 
 0	1	2	3	4	
 
 It was hard for me to pay attention when I had pain.						
 
 0	1	2	3	4	
 
 It was hard for me to run when I had pain.						
 
 0	1	2	3	4	
 
 It was hard for me to walk one block when I had pain.						
 
 0	1	2	3	4	
 
 It was hard to have fun when I had pain.						
 
 0	1	2	3	4	
 
 It was hard to stay standing when I had pain.						
 
 0	1	2	3	4	
  
		Never	Almost Never	Sometimes	Often	Almost Always	I felt angry when I had pain.		0	1	2	3	4	I had trouble doing schoolwork when I had pain.		0	1	2	3	4	I had trouble sleeping when I had pain.		0	1	2	3	4	It was hard for me to pay attention when I had pain.		0	1	2	3	4	It was hard for me to run when I had pain.		0	1	2	3	4	It was hard for me to walk one block when I had pain.		0	1	2	3	4	It was hard to have fun when I had pain.		0	1	2	3	4	It was hard to stay standing when I had pain.		0	1	2	3	4																																
	Never	Almost Never	Sometimes	Often	Almost Always																																																																																										
I felt angry when I had pain.																																																																																															
0	1	2	3	4																																																																																											
I had trouble doing schoolwork when I had pain.																																																																																															
0	1	2	3	4																																																																																											
I had trouble sleeping when I had pain.																																																																																															
0	1	2	3	4																																																																																											
It was hard for me to pay attention when I had pain.																																																																																															
0	1	2	3	4																																																																																											
It was hard for me to run when I had pain.																																																																																															
0	1	2	3	4																																																																																											
It was hard for me to walk one block when I had pain.																																																																																															
0	1	2	3	4																																																																																											
It was hard to have fun when I had pain.																																																																																															
0	1	2	3	4																																																																																											
It was hard to stay standing when I had pain.																																																																																															
0	1	2	3	4																																																																																											
PROMIS GI Symptoms (patient $\geq$ 14 years)	
In the past 7 days...
 
My poop was loose or watery          I rushed to the bathroom to avoid an accident          I had blood in my poop          I had a stomachache
 
Each of the four items is scored as 1 (Never), 2 (Rarely), 3 (Sometimes), 4 (Often), and 5 (Always)
																																																																																														
Pediatric Ulcerative Colitis Activity Index (PUCAI) - Patient Version	
"These are questions about how your child has been feeling over the past 24 hours"
 
Question 1. How much has your stomach been hurting in the past 24 hours?
 
 
 Not at all
 
 Hurting somewhat, but I can ignore it
 
 Hurting very much; it is always on my mind
 
																																																																																														

	
Question 2. Did you have stools containing blood over the past 24 hours?
 
 Not at all  A small amount only, in less than half of stools  Small amount with most stools  Large amount, in more than half of stools
 
Question 3. Which of the following best describes your stool over the past 24 hours?
 
 Solid  Soft (passes easily)  Watery
 
Question 4. Number of stools per 24 hours (from yesterday this time until now). Please remember that if you are having small frequent stools one after another without having left the bathroom, it counts as one stool.
 
 0-2  3-5  6-8  More than 8
 
Question 5. Did you wake up overnight because you needed to move your bowels?
 
 No  Yes
 
Question 6. How has your activity level been over the past 24 hours?
 
 I have been able to do my usual activities without a problem  Sometimes I have had to stop what I wanted to do because I was not feeling well  I have not been able to do my usual activities at all

Short Crohn's Disease Activity Index (SCDAI) – Patient Version	
These questions refer to the time period from when you awoke yesterday to when you awoke today.
 
1. Please indicate the number of liquid or soft stools that you have had (answer: open ended frequency)

	
2. Please indicate your abdominal pain level (answer choice: 0=none; 1=mild; 2=moderate; 3=severe)
 
3. Please rate your general well-being (answer choice: 0=generally well; 1= slightly under par; 2=poor; 3=very poor; 4=terrible)

--	---

